3.5 Visit 4 Interim Treatment Testing

About two weeks later, the patient will return after a twelve-hour fast and avoidance of alcohol for 24 hours. The patient will be asked about any changes in eligibility criteria, study medication dosing, concomitant medications and adverse events. Vital signs will be obtained. The patient will turn in any remaining study medication and receive a new supply. The patient will bring in a single, random stool sample and will be given a new stool collection kit to bring in a sample at the next visit. The patient will return the bowel pattern diary and receive a new bowel pattern diary. Blood will be obtained for C4, FGF19 and pk analysis. Urine will be obtained for a pregnancy test for females of child-bearing potential.

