4.4 Patient Withdrawal and Replacement

If a patient is pregnant, the patient will be withdrawn from study treatment immediately.

A patient may be withdrawn for any treatment related adverse event or clinically significant findings in clinical labs or other vital signs that are deemed by the investigator to pose an unacceptable risk to the patient. If the study is interrupted due to any of the criteria listed above, the patient may undergo unscheduled assessments to evaluate his/her status. Additional subsequent visits may be required to assess event outcomes.

Study treatment may be discontinued, interrupted or dose reduced for any grade 3 adverse event that is possibly or probably related to study treatment. Study treatment will be discontinued for any grade 4 adverse event that is possibly or probably related to study treatment

Patients may also be discontinued from the study at any time for any of the following reasons:

- Adverse event
- Death
- Lost to follow-up
- Investigator decision
- Pregnancy
- Protocol deviation
- Study terminated by Sponsor
- Withdrawal by subject

A patient may be withdrawn from the study at any time due to the following adverse events based on the known safety profile and mechanism of the drug:

- Dehydration requiring hospitalization
- A laboratory result of total cholesterol and triglycerides $> 2 \times$ ULN
- Allergic reaction requiring hospitalization

A patient may be withdrawn from the study at any time due to the following adverse events:

- A laboratory result of ALT or AST $> 3 \times$ ULN, total direct bilirubin $> 2 \times$ ULN or serum creatine > 2.5 ULN
- Abnormal cardiac findings such as a clinically significant abnormal heart rate or rhythm, left bundle branch block with QRS interval > 110 msec or first-degree AV block with PR interval > 220 msec.

A patient may be withdrawn by the investigator or the sponsor if enrollment in the study is deemed inappropriate, the study plan is violated, or for administrative and/or safety reasons.

A patient may elect to discontinue study participation at any time for any reason without prejudice to his/her

future medical care by the physician or at the institution. The investigator will document the specific reason why consent was withdrawn.

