7.2 Statistical Analysis

Effects of treatment will be compared using Intent-to-Treat principles using ANCOVA with BMI, gender and baseline fasting C4 as covariates. In order to reach 30 subjects, accrual will be set at 36 to replace any volunteer(s) who withdraw prior to taking less than 1 day of dosing. Any Subject who receives more than 1

day of dosing will be consider completed using the Intent-to-Treat analysis.

Primary endpoints are change in fasting serum C4 levels from baseline to Day 28 and change in stool consistency based on Bristol Stool Form Scale, BSFS from baseline to Day 28.

Secondary endpoints are

- Absolute change in stool consistency from baseline to Day 14 and Day 28 of treatment
- Average daily stool consistency score at Day 14 and Day 28 of treatment
- Maximum abdominal pain score rated by patient using an 11-point scale, 0 to 10 inclusive with 0 as none and 10 as worst imaginable pain
- Absolute change in abdominal pain from baseline to Day 14 and Day 28 of treatment
- Number of bowel movements per week
- Change in total fecal bile acid concentration between baseline and Day 28
- Proportion of fecal secretory (CDCA+ DCA) bile acid as measured in a single, random stool sample by a validated laboratory assay.
- Proportion of fecal primary (CDCA + CA) bile acid as measured in a single, random stool sample by a validated laboratory assay.
- Total fecal bile acid concentration in a single, random stool sample as measured by a validated laboratory assay.
- Total aldafermin concentration in serum as measured by a validated laboratory assay

Adverse events (AEs) will be listed and summarized by system organ class and preferred term, as well as according to severity and causality/relationship to study treatment.

Observed values for clinical laboratory tests, vital signs and safety 12-lead ECGs will be summarized by treatment. Observed values will be classified as normal, abnormality that is not clinically significant, and clinically significant abnormality by treatment.

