8.4 Safety Review Plan

Study progress and safety will be reviewed quarterly (and more frequently, if needed). Progress reports including patient recruitment, retention/attrition, and AEs will be provided to the Independent Monitor every year. An annual report will be compiled and will include a list and summarization of AEs. In addition, the annual report will address:

1. Whether AE rates are consistent with pre-study assumptions;
2. Reason for dropouts from the study;
3. Whether all participants met entry criteria;
4. Whether continuation of the study is justified on the basis that additional data are needed to accomplish the stated aims of the study; and
5. Conditions whereby the study might be terminated prematurely (i.e., voluntary dropout of > 40% of cohort).

The annual report will be reviewed by the independent monitor and will be forwarded to the IRB on an annual basis.

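### Section 7.2 counts any patient with more than 1 day of dosing as completed but gives no way to score a missing Day 28 value, and neither co-primary analysis uses the Day 14 data already collected

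*Combined protocol and SAP*

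**What the plan says.** Section 7.2 names one efficacy model, "using ANCOVA with BMI, gender and baseline fasting C4 as covariates", under Intent-to-Treat principles. The outcomes are set there too: "Primary endpoints are change in fasting serum C4 levels from baseline to Day 28 and change in stool consistency", the latter on the Bristol scale and also to Day 28.

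The same section sets the rule for early leavers: "accrual will be set at 36 to replace any volunteer(s) who withdraw prior to taking less than 1 day of dosing". Anyone with more than 1 "day of dosing will be consider completed using the Intent-to-Treat analysis".

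Day 28 C4 comes from the Visit 5 blood sample, and the last diary is handed in at that visit (section 3.6). At Visit 4, about Day 14, the first treatment diary is handed in and "Blood will be obtained for C4, FGF19 and pk analysis" (section 3.5).

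Section 4.4 ("Patients may also be discontinued from the study at any time for any of the following reasons") lists eight reasons for leaving. It offers optional unscheduled assessments but requires no Day 28 measurement. Section 8.4 mentions "voluntary dropout of > 40% of cohort" as an example of a condition for early termination. No section gives an expected drop-out rate, an imputation method, a repeated-measures model or a sensitivity analysis.

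**The concern.** Calling a patient completed does not create a Day 28 value. Someone who leaves on Day 15 belongs to the Intent-to-Treat set by the section 7.2 definition, yet has no Day 28 C4 and may have no returned diary for the second fortnight. An ANCOVA of change to Day 28 has no outcome for that patient and, unless told otherwise, omits the record. Losses after the first day are not replaced either.

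In a diarrhoea trial, patients who leave after two weeks may well be those with poor stool response or poor tolerance. If so, the patients left for comparison are no longer balanced by randomisation, and the estimated effect can move either way depending on which arm loses them. The Day 14 values that could correct for much of this are collected but unused in the co-primary analyses. With no rule written down, the handling could also be chosen after unblinding.

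**Working it through.** **1. Reproducing the plan's figures.** Inputs: two-sided α = 0.05, 80% power, and the means and SDs in section 7.1. Power comes from the two-sample t-test with 2n − 2 degrees of freedom and non-centrality (Δ/SD)·√(n/2), solved for Δ.

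- n = 9 per group: 1.407 SD. C4: 1.407 × 45.6 = 64.2 ng/mL (Table 1: 64.1). Stool form: 1.407 × 1.12 = 1.58 (Table 1: 1.58).
- n = 6 per group: 1.796 SD. C4: 1.796 × 50.6 = 90.9 ng/mL (Table 2: 90.8). Stool form: 1.796 × 0.6 = 1.08 (Table 2: 1.08).
- n = 15 per group: 1.06 SD, which is 1.06 × 1.12 = 1.19 stool-form points with the Table 1 SD. This is the true effect assumed below.

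**2. Who can be scored at Day 28.**

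| Patient | Day 14 data | Day 28 data | Rule in the plan |
|---|---|---|---|
| Leaves around the first day | no | no | replaced (36 − 30 = 6 spare places) |
| Leaves later, before Visit 4 | no | no | counted as completed; no scoring rule |
| Leaves between Visits 4 and 5 | C4 and diary | no C4; last diary not handed in | counted as completed; no scoring rule |
| Stops drug, attends Visit 5 | yes | yes | scored normally |

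**3. Loss of numbers alone.** Same t-test formula at 1.06 SD: 80% power with 15 per arm, 77% with 14, 70% with 12, 61% with 10 and 56% with 9 (15 × 0.6, a 40% loss).

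**4. Why selective loss biases the Day 28 estimate.** Let β be the slope of the Day 28 value on the Day 14 value, given treatment and covariates. The estimate that uses Day 14 is γ + β·δ14(all patients with Day 14 data). The completers' ANCOVA equals γ + β·δ14(completers only). The difference is β × [δ14(completers) − δ14(all)].

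Assumed correlations are 0.5 between baseline and each later visit and 0.7 between Days 14 and 28. With the outcome's own baseline in the model, β = (0.7 − 0.5²)/(1 − 0.5²) = 0.45/0.75 = 0.6. So 60% of any distortion in the Day 14 contrast among completers passes into the Day 28 estimate.

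**5. Size for stool form.** Simulation: 15 per arm, true effect 1.06 SD, 5 of 30 (17%) lost after Day 14, outcome's own baseline in the model. The lower end of each range is loss only partly driven by Day 14 response. The upper end is loss of exactly the worst Day 14 responders.

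| Who leaves | Shift in completers' estimate | In stool-form points | Type I error |
|---|---|---|---|
| Random | none | 0 | no inflation |
| Poor responders, either arm | 8–15% too small | 0.10–0.18 (0.08 and 0.15 × 1.19) | 4–5% |
| Active-arm non-responders only | 16–23% too large | 0.19–0.27 (0.16 and 0.23 × 1.19) | 7–10% |

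The estimate that uses Day 14 had at most about 1% bias in these settings, with type I error of about 4–5% when small-sample degrees of freedom were used. Under random loss of 5 of 30, power was 66% for the ANCOVA and 68% for the repeated-measures estimate, here without the outcome's own baseline in the model.

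**6. Sensitivity.**

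- *Weaker link.* If all three visits share one correlation r, β falls to (0.7 − 0.49)/(1 − 0.49) = 0.41 at r = 0.7 and 0.25/0.75 = 0.33 at r = 0.5. Large-sample attenuation at 10/20/30% loss is then 8/13/17% and 6.5/10.5/13.5%. Inflation is 5–13% when 10–30% of the active arm's worst responders leave.
- *Fewer losses.* With one or two active patients lost and only a partial link to response, type I error stays at about 5%.
- *Covariates.* The planned model adjusts for baseline C4, not baseline stool form. Without the stool baseline, partial selection gave −0.94 SD (about 12% too small) or −1.31 SD (about 23% too large, type I error 8%). The strictest selection gave −0.80 SD (1 − 0.80/1.06 = 25% too small) or −1.41 SD (1.41/1.06 − 1 = 33% too large, type I error 14%). These last two are close to a worst case.

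**The case against.** The strongest reply is that the plan is silent, not wrong, and several stronger readings fail.

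- A reader might infer that the plan prescribes a complete-case analysis. It does not. Dropping patients is what the named model does by default. The completed label could equally be taken to mean carrying a value forward, which would be a different problem. Day 28 stool form has no stated averaging window, so a partial diary might count. What stands is that no reading is fixed in advance.
- A reader might infer that Day 14 data are ignored throughout. Day 14 stool change, average stool score and pain change are secondary endpoints. Day 14 is unused in the co-primary analyses, and Day 14 C4 feeds no endpoint.
- A reader might infer that both co-primaries are shown to be biased. Only stool form was modelled. Bias in C4 depends on how closely C4 follows the reasons for leaving, which the documents do not give, and its own baseline is already in the model.
- A reader might expect distortions of 30% and type I error above 10%. Those need nearly perfect selection of non-responders and no stool baseline in the model. Inflated type I error also needs losses confined to the active arm.
- The 40% in section 8.4 is a termination example, not an expected rate. Losses in a 28-day trial may be few, and rescue loperamide and continued sequestrants may hold some patients in.

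The remedy has limits too. It helps chiefly those lost between Visits 4 and 5. In 30 patients it needs a small-sample correction: plain maximum-likelihood variances with a normal reference gave 7–13% type I error. These objections reduce the size and shape the fix. They do not remove the gap.

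**Conclusion.** The point holds for the co-primary analyses. Section 7.2 puts patients without a Day 28 value in the analysis but provides no way to score them, and it leaves out Day 14 data that would largely correct for loss related to earlier response.

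For stool form, the size is the 8–15% attenuation or 16–23% inflation shown above. It rests on assumptions not in the documents: 5 of 30 lost after Visit 4, a true effect of 1.06 SD, the stated correlations, loss driven by Day 14 response, and the stool baseline in the model. With random loss there is no bias, and the ANCOVA gives up only a little power to the repeated-measures model. For C4, the gap in the plan is the same but the size of any bias is not established. The change is well worth making because it costs so little, but the documents do not show that the trial's result would be overturned.

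**What to change.** In section 7.2 and the synopsis:

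1. Make the primary analysis of each co-primary a repeated-measures model on change at Day 14 and Day 28. Fit treatment, visit, treatment-by-visit, the planned covariates and the outcome's own baseline, with unstructured covariance. Use REML with Kenward-Roger or similar small-sample degrees of freedom.
2. Take the Day 28 treatment contrast as the primary estimate.
3. Replace the completed sentence with an analysis-set definition: every randomised and dosed patient with any post-baseline value, using the diary data that were returned. This also settles the case of exactly 1 day of dosing, which the present wording leaves open.
4. Report the Day 28 ANCOVA as a sensitivity analysis.

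The cost is statistical wording, best settled before unblinding. It needs no new visits, samples or patients. The downsides are a slightly more complex model, reliance on missing at random, and little help for patients lost before Visit 4.

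### Calling a patient with more than one day of dosing completed does not supply a Day-28 value; the plan needs a missing-data rule, and a repeated-measures model would reduce, though not remove, dropout bias

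*Combined protocol and SAP*

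**What the plan says.** Combined protocol and SAP, section 7.2, gives the analysis as "Effects of treatment will be compared using Intent-to-Treat principles using ANCOVA with BMI, gender and baseline fasting C4 as covariates". The time point is fixed: "Primary endpoints are change in fasting serum C4 levels from baseline to Day 28", with stool consistency over the same interval as the second primary endpoint. Anyone with more than one day of dosing "will be consider completed using the Intent-to-Treat analysis". Accrual is 36 in order to reach 30, so as to "replace any volunteer(s) who withdraw prior to taking less than 1 day of dosing".

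Neither section 7 nor the synopsis gives an imputation method, a last-observation rule, a repeated-measures model or a sensitivity analysis. Section 4.4 lists many routes out of the study and allows unscheduled assessments, but requires no Day-28 assessment after withdrawal.

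On-treatment data do exist. At Visit 4, about two weeks after randomization, section 3.5 says "Blood will be obtained for C4, FGF19 and pk analysis". Section 6.8 has stool form recorded in a daily diary. The only dropout figure is in section 8.4, where "voluntary dropout of > 40% of cohort" is an example of a condition for ending the study early.

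**The concern.** A patient who leaves on day 3 is completed by definition but has no Day-28 C4. The analyst must then leave that patient out, which is not intention to treat, or choose a fill-in rule after the fact. With 15 patients per arm, a few such decisions can move the result.

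Dropout that differs by arm is plausible from the documents, though not shown by them. In the earlier functional constipation study (section 1.3), 1 mg aldafermin gave faster 48-hour colonic transit than placebo (4.29 v 3.36, P = 0.001) and numerically more bowel movements (8.0 v 5.1 per week, P = 0.178). Section 4.4 names dehydration requiring hospitalization among the withdrawal reasons tied to the drug's mechanism. If active-arm patients whose diarrhea worsens leave, and only the rest are analysed, the drug looks better than it is on stool form.

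The replacement sentence cannot be applied as written. Nobody can withdraw before taking less than one day of drug, and a patient with exactly one day is neither replaceable nor completed.

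**Working it through.** **1. The plan's own figures.** Section 7.1 gives detectable differences at about 80% power, two-sided alpha 0.05. For a two-sample t-test, power = P(|T| > t(0.975, 2n−2)), where T is noncentral t with noncentrality d√(n/2).

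- n = 9 per group: C4 64.1/45.6 = 1.41 SD, power 79.9%; stool form 1.58/1.12 = 1.41 SD, power 80.2%.
- n = 6 per group: C4 90.8/50.6 = 1.79 SD, power 80.0%; stool form 1.08/0.6 = 1.80 SD, power 80.2%.

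The absolute differences reproduce. (Table 1 prints 1.34 SD beside C4; 64.1/45.6 is 1.41.) At 15 per arm the same formula gives 80% power at 1.06 SD, which for C4 is 1.06 × 45.6 = 48.3 ng/mL.

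**2. Power if only patients with Day-28 data are analysed** (true difference 1.06 SD):

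| Per arm with Day-28 data | Power |
|---|---|
| 15 | 80% |
| 14 | 77.0% |
| 13 | 73.7% |
| 12 (20% lost) | 69.9% |
| 10 | 61.1% |
| 9 (40% lost) | 56.1% |

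The accrual margin is 36 − 30 = 6, and it covers only the withdrawals in the replacement sentence. Later losses are not allowed for.

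**3. Bias with 2 to 4 dropouts.** Simulation with no true effect, 15 per arm. Assumed: correlation with baseline 0.5; Day 14 to Day 28 correlation 0.7 to 0.85. Bias is toward the drug.

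| Assumed dropout | Bias, Day-28 ANCOVA in patients with data | Type I error |
|---|---|---|
| 2–4 worst Day-14 patients, active arm only | 0.10–0.27 SD | 6–13% |
| 2–4 active-arm patients, probability rising with Day-14 value | 0.05–0.15 SD | 5–7% |
| As above, 3 active v 2 placebo | about 0.03 SD | not reported |
| 2 or 3 worst from each arm | about 0 | 5–8% |
| Random | about 0 | not reported |

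In the first row, a likelihood estimate using Day 14 had bias within 0.01 SD and type I error of 4.2 to 5.0%. The upper end, 0.27 SD, is 0.27 × 45.6 = 12.3 ng/mL of C4, or 0.27/1.06 = 25% of the detectable difference.

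**4. Limits of the repeated-measures model.** A second simulation used heavier loss (about 20–25% of all patients without Day-28 data), a true C4 difference of 48.3 ng/mL, baseline correlation 0.5, and no BMI or gender. Bias in ng/mL at Day 14 to Day 28 correlation 0.7, with the range over 0.5 to 0.85 in brackets:

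| Dropout depends on | Lost before Day 14 | Day-28 ANCOVA | Repeated measures |
|---|---|---|---|
| Nothing, or baseline C4 | any share | about 0 | about 0 |
| Day-14 value | none | 14 (8–19) | about 0 |
| Day-14 value | half | 14 (8–19) | 5.6 (3.3–7.5) |
| Day-14 value | all | 14.2 (7.9–18.7) | 14.2 (7.9–18.7) |
| Unseen Day-28 value | none | about 23 | 16.1 (9.7–20.9) |

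These biases are larger than in step 3 (14/45.6 = 0.31 SD) under a different dropout model with more patients lost. The run serves to compare the two methods, not to predict this trial.

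**The case against.** Several stronger readings are tempting, and the documents do not support them.

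- **That repeated measures avoids the bias.** It does so only if dropout depends on observed data. A patient who leaves on day 2 has no post-baseline C4, so the model gains nothing on C4 for that patient. If dropout depends on unseen values, bias remains.
- **That a Day-28 ANCOVA is always biased.** It is unbiased under random or baseline-driven dropout, and close to unbiased if similar patients leave both arms.
- **That the plan excludes dropouts.** It does not say so. It gives no rule, and a Day-28-only analysis is an inference. Section 4.4 also separates stopping treatment from leaving the study, so a patient who stops the drug could still attend Visit 5.
- **That Day-14 data are ignored.** Day-14 stool consistency and abdominal pain are secondary endpoints. It is the Day-14 C4 that has no listed endpoint, and no Day-14 value has a role in the primary analysis.
- **That 40% dropout is expected.** The figure in section 8.4 is a stopping example, not a planning rate.

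The mechanism is also weaker for C4 than for stool form. C4 is a laboratory value, assignment is blinded, and C4 is not among the withdrawal reasons in section 4.4. Under random dropout the gain from the model is small, about 0 to 8 power points.

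All of this stands and limits the size of the claim. It does not remove the gap: the plan has no rule for a missing Day-28 value, and the completed label hides that. In every scenario run, the repeated-measures estimate was no more biased than the Day-28 ANCOVA, apart from simulation noise.

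**Conclusion.** The point holds in limited form and should be corrected before the analysis. The completion rule does not yield a Day-28 value, and the replacement rule cannot be applied as worded.

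For 2 to 4 dropouts, the bias of an analysis restricted to patients with Day-28 data runs from about 0 to 0.15 SD in the milder patterns to about 0.1 to 0.3 SD, with type I error of 6 to 13%, if only the worst active-arm patients leave. Heavier loss or dropout driven by unseen values could give more. All of these sizes rest on assumed dropout patterns and correlations.

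Repeated measures is the better primary analysis because it uses data already planned. It reduces dropout bias and does not cure it.

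**What to change.** 1. **Analysis set.** Include all randomised patients who took at least one dose, in the arm assigned. Delete the statement that dosed patients count as completed.
2. **Data.** Seek Day-28 C4 and diary data from patients who stop treatment but remain in the study.
3. **Primary model.** Use a repeated-measures model: Day 14 and Day 28 for C4, weekly diary means for stool form. Terms are treatment, visit, treatment-by-visit, the endpoint's own baseline and the stated covariates. The Day-28 contrast is primary.
4. **Sensitivity.** Prespecify an analysis for data not missing at random. It also has to cover patients lost before Day 14, for whom the model has no on-treatment C4.
5. **Replacement.** Reword the rule so that it can be applied, limits replacement to patients who withdraw before the first dose, and leaves no dosed patient unclassified. Section 5.5 assigns the randomisation number at study treatment administration, and section 3.4 has the first dose observed at Visit 3, so few randomised patients would then be replaceable. Restate the allowance from 30 to 36 to match.

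The cost is plan wording, modest programming and an effort to keep patients attending after they stop treatment. No new visit or assay is needed.
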